5.4.3.2 Abortions

A spontaneous abortion should be classified as a serious adverse event (as the Sponsor considers abortions to be medically significant), recorded on the Adverse Event eCRF, and reported to the Sponsor immediately (i.e., no more than 24 hours after learning of the event; see Section 5.4.2).

If a therapeutic or elective abortion was performed because of an underlying maternal or embryofetal toxicity, the toxicity should be classified as a serious adverse event, recorded on the Adverse Event eCRF, and reported to the Sponsor immediately (i.e., no more than 24 hours after learning of the event; see Section 5.4.2). A therapeutic or elective abortion performed for reasons other than an underlying maternal or embryofetal toxicity is not considered an adverse event.

All abortions should be reported as pregnancy outcomes on the paper Clinical Trial Pregnancy Reporting Form.

5.4.3.3 Congenital Anomalies/Birth Defects

Any congenital anomaly/birth defect in a child born to a female patient exposed to study drug should be classified as a serious adverse event, recorded on the Adverse Event eCRF, and reported to the Sponsor immediately (i.e., no more than 24 hours after learning of the event; see Section 5.4.2).

5.5 FOLLOW-UP OF PATIENTS AFTER ADVERSE EVENTS

5.5.1 Investigator Follow-Up

The investigator should follow each adverse event until the event has resolved to baseline grade or better, the event is assessed as stable by the investigator, the patient is lost to follow-up, or the patient withdraws consent. Every effort should be made to follow all serious adverse events considered to be related to study drug or trial-related procedures until a final outcome can be reported.

During the study period, resolution of adverse events (with dates) should be documented on the Adverse Event eCRF and in the patient's medical record to facilitate source data verification.

All pregnancies reported during the study should be followed until pregnancy outcome.

5.5.2 Sponsor Follow-Up

For serious adverse events, adverse events of special interest, and pregnancies, the Sponsor or a designee may follow up by telephone, fax, email, and/or a monitoring visit to obtain additional case details and outcome information (e.g., from hospital discharge summaries, consultant reports, autopsy reports) in order to perform an independent medical assessment of the reported case.

5.6 ADVERSE EVENTS THAT OCCUR AFTER THE ADVERSE EVENT REPORTING PERIOD

The Sponsor should be notified if the investigator becomes aware of any serious adverse event that occurs after the end of the adverse event reporting period (defined as 28 days the final dose of study treatment), if the event is believed to be related to prior study drug treatment. These events should be reported through use of the Adverse Event eCRF. However, if the EDC system is not available, the investigator should report these events directly to the Sponsor or its designee, either by faxing or by scanning and emailing the paper Clinical Trial Serious Adverse Event/Adverse Event of Special Interest Reporting Form using the fax number or email address provided to investigators.

5.7 EXPEDITED REPORTING TO HEALTH AUTHORITIES, INVESTIGATORS, INSTITUTIONAL REVIEW BOARDS, AND ETHICS COMMITTEES

The Sponsor will promptly evaluate all serious adverse events and adverse events of special interest against cumulative product experience to identify and expeditiously

communicate possible new safety findings to investigators, IRBs, ECs, and applicable health authorities based on applicable legislation.

To determine reporting requirements for single adverse event cases, the Sponsor will assess the expectedness of these events through use of the reference safety information in the documents listed below:

Drug	Document
GDC-9545	GDC-9545 Investigator's Brochure
Palbociclib	Palbociclib Summary of Product Characteristics
Anastrozole	Anastrozole Summary of Product Characteristics

The Sponsor will compare the severity of each event and the cumulative event frequency reported for the study with the severity and frequency reported in the applicable reference document.

Reporting requirements will also be based on the investigator's assessment of causality and seriousness, with allowance for upgrading by the Sponsor as needed.

6. STATISTICAL CONSIDERATIONS AND ANALYSIS PLAN

Efficacy analyses will consist of all randomized patients, unless specified otherwise. Safety analyses will include all randomized patients who received any amount of study treatment.

6.1 DETERMINATION OF SAMPLE SIZE

The sample size is determined by the primary efficacy endpoint, central assessment Ki67 change from baseline to Week 2 (see details in Section 6.4.1). Approximately 202 patients will need to be randomized in a 1:1 ratio to either the experimental arm (GDC-9545) or control arm (anastrozole) to allow for 80% power to detect an 8% improvement for mean Ki67 change in 2 weeks from -75% in the control arm to -83% in the experimental arm at one-sided 10% level of significance. This target improvement also corresponds to an effect size of 0.3. Based on Cohen's interpretation (Cohen 1988), an effect size of 0.3 represents a small to medium effect and a 21% non-overlap between the two treatment arms.

Patients with missing central Ki67 score at baseline and/or at Week 2 will be excluded from the analysis of the primary efficacy endpoint. For both experimental and control arms, a 6% missing Ki67 rate is assumed. Thus, a total of approximately 215 patients is projected to be enrolled to account for patients with missing Ki67 scores.

6.2 SUMMARIES OF CONDUCT OF STUDY

Study enrollment, duration, study drug discontinuation, and study discontinuation, as well as reasons for study drug discontinuation and study discontinuation, will be listed and summarized for each treatment arm. Major protocol deviations, including major deviations of inclusion/exclusion criteria, will also be listed and summarized for each treatment arm.

6.3 SUMMARIES OF TREATMENT GROUP COMPARABILITY

Evaluation of treatment group comparability between the treatment arms will include demographic summaries, stratification factors, patient treatment history, and other baseline disease characteristics.

Continuous data will be summarized using means, standard deviations, medians, and ranges. Categorical data will be summarized by counts and proportions.

6.4 EFFICACY ANALYSES

Unless specified otherwise, the analysis population for an efficacy analysis will consist of all randomized patients, with patients grouped according to their assigned treatment.

6.4.1 Primary Efficacy Endpoint

The primary efficacy endpoint for this study is Ki67 score change during the window-of-opportunity phase, defined as the mean change of Ki67 score from baseline to Week 2. Ki67 score will be centrally assessed and measured in percentage score. All Ki67 scores will be log-transformed before analysis, and 0.1 will be added to all raw Ki67 scores before log-transformation to handle zero raw Ki67 scores.

Mean Ki67 change at Week 2 will be summarized in original percentage scale for each arm, and corresponding 95% CI will be calculated by normal approximation. The change in mean Ki67 score between the experimental arm and control arm will be compared through the use of the z-test. Patients with missing central Ki67 scores at baseline and/or Week 2 will be excluded from the analysis.

The analysis of the primary efficacy endpoint will take place when approximately 202 patients have been randomized and have complete central Ki67 scores for the analysis at both baseline and Week 2.

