Tumor tissue should be of good quality based on total and viable tumor content: Samples must contain a minimum of 500 viable tumor cells that preserve cellular context and tissue architecture regardless of needle gauge or retrieval method. Samples collected via resection, core-needle biopsy (at least three cores, embedded in a single paraffin block), punch, or forceps biopsy are acceptable. Fine-needle aspiration (defined as samples that do not preserve tissue architecture and yield cell suspension and/or smears), brushing, and lavage samples are not acceptable.

Archival tumor tissue from prior diagnostic FFPE cores may be used; however, if archival tumor tissue is unavailable or is determined to be unsuitable for required testing, a pretreatment fresh tumor biopsy is required. A pretreatment tumor biopsy may also be performed if a patient's archival tissue test results do not meet eligibility criteria. If a pretreatment tumor biopsy is determined to be required, two FFPE core-needle biopsies embedded in a single paraffin block and one freshly frozen optimal cutting temperature (OCT) core-needle biopsy will be required.

- **After 2 weeks of treatment and at the time of surgery.** FFPE and non-FFPE samples will be prepared from the newly collected tumor biopsies and surgical resection.

Two FFPE core-needle biopsies embedded in a single paraffin block and one freshly frozen OCT core-needle biopsy are required on Day 15 (+1 day).

For the post-treatment tissue sample collected at surgery, an FFPE tumor block from surgical resection is required. If a tumor block cannot be submitted for various reasons (e.g., the tumor tissue is not sufficient at surgical resection or due to site restrictions), approximately 15–20 paraffin embedded, unstained slides from the surgical specimen are required. A freshly frozen OCT tumor tissue sample at surgery is required, unless not clinically feasible.

If the patient has pCR at time of surgery, tumor surgical specimens will no longer required.

All tumor tissue samples collected during the study will be sent to one or several central laboratories or to the Sponsor or a designee for analysis.

A detailed description of tissue quality requirements and procedures for collection, handling and shipping of tumor tissue samples will be provided in a separate laboratory manual.

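### The primary Ki67 analysis is complete-case only, and nothing planned tests whether missing scores distort the arm comparison

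*Combined protocol and SAP*

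**What the plan says.** Section 6.4.1 takes centrally assessed Ki67, adds 0.1, log-transforms it, and compares the change to Week 2 between arms with a z-test that has no covariates or stratification factors. On missing scores it says: "Patients with missing central Ki67 scores at baseline and/or Week 2 will be excluded from the analysis". Section 6.1 and the synopsis repeat the exclusion.

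Section 6.4 gives the general rule that "the analysis population for an efficacy analysis will consist of all randomized patients". That sentence opens by allowing exceptions where specified, as does the start of section 6.

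Section 6.1 plans for the loss of numbers. It assumes 6% missing in each arm and raises 202 to about 215.

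Other endpoints get more. In section 6.4.2, a patient with no post-baseline tumor assessment counts as a non-responder for ORR. In section 6.5.2, the amount of missing PRO data is to be reported at each timepoint. Section 6.2 summarizes treatment and study discontinuations by arm with reasons. Nothing comparable is specified for missing Ki67 scores.

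**The concern.** A complete-case comparison estimates the treatment effect without bias only if, within each arm, patients who lack a score would have had the same Ki67 change on average as those who have one. The unadjusted z-test does not even condition on baseline Ki67, T status or PgR status, all known at randomization.

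There are credible ways for this to fail. Patients and investigators know the arm, so declining the Day 15 biopsy or stopping early could depend on it. A tumor that responds strongly might yield too little assessable tissue at Week 2. The first mechanism could push either way; the second would tend to work against the more active drug.

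Separately, section 4.5.10 lets a site with approved local testing randomize once shipment of tissue to the central laboratory is confirmed. A patient can therefore be randomized and later prove to have no central baseline, and her valid Week 2 score is then discarded. Because this arises before treatment, it mainly wastes information.

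The planned effect is small in SD units, so a modest distortion could take up a noticeable share of it. Raising enrollment to 215 restores precision but does not address bias.

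**Working it through.** **Inputs (section 6.1).** The test is run "at one-sided 10% level of significance". The design claims "80% power to detect an 8% improvement for mean Ki67 change in 2 weeks", with assumed mean changes of −75% on anastrozole and −83% on GDC-9545. On the standardized scale the section adds: "This target improvement also corresponds to an effect size of 0.3". For the evaluable number it states: "Approximately 202 patients will need to be randomized in a 1:1 ratio". It assumes 6% missing per arm and about 215 enrolled.

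**Step 1: reproduce the plan's figures.**
- Per arm: n = 2 × (1.2816 + 0.8416)² / 0.3² = 100.2, so 101, or 202 in total.
- Power at 101 per arm: Φ(0.3 × √50.5 − 1.2816) = 80.2%.
- Enrollment: 202 / 0.94 = 214.9, so 215.

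Both figures stand.

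**Step 2: effect of unequal missingness.** Assumption: missing patients have a Ki67 change 1 SD better than their arm's overall average. If a fraction m is missing, the observed mean is worse than the true arm mean by m/(1 − m) SD. The shift in the comparison is the difference between arms. Power applies when more patients are missing in the experimental arm; one-sided type I error applies when more are missing in the control arm.

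| Missing, higher vs lower arm | Shift (SD) | Share of 0.3 | Power | Type I error |
|---|---|---|---|---|
| 6% vs 6% | 0 | 0% | 80% | 10% |
| 7% vs 5% | 0.0753 − 0.0526 = 0.023 | 8% | 75% | 13% |
| 9% vs 3% | 0.0989 − 0.0309 = 0.068 | 23% | 64% | 21% |

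Formulas, with b the shift: power = Φ((0.3 − b) × √50.5 − 1.2816); type I error = 1 − Φ(1.2816 − b × √50.5). For 9% vs 3%: Φ(0.232 × 7.106 − 1.2816) = Φ(0.367) = 0.64, and 1 − Φ(1.2816 − 0.483) = 0.21. These hold 101 evaluable patients per arm.

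**Step 3: equal rates, but informative in one arm only.** Let the missing patients of one arm differ by s SD from that arm's observed patients. The bias is m × s. The standard error is √(2/101) = 0.141 SD. At m = 6%:
- s = 0.5: bias 0.03 SD (10% of target); type I error 14.3% or power 73.8%, depending on direction.
- s = 1.0: bias 0.06 SD (20%); 19.6% or 66.4%.
- s = 2.0: bias 0.12 SD (40%); 33.4% or 49.9%.

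**Step 4: what would overturn a result at the design effect?** The critical value is 1.2816 × 0.141 = 0.180 SD. An observed 0.30 SD loses significance when m × s exceeds 0.30 − 0.180 = 0.120. That needs s of about 2.0 SD at 6% missing, 1.2 SD at 10%, or 0.8 SD at 15%.

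The documents give no SD. If the 0.3 is on the log scale and the percentages are geometric-mean changes, the SD is ln(0.25/0.17)/0.3 = 1.29. Suppose every missing experimental patient had no Ki67 change at all while missing controls resembled observed controls. Then s = ln(1/0.17)/1.29 = 1.38, the bias is 0.06 × 1.38 = 0.083, and the effect falls to 0.217 SD, still above 0.180.

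**The case against.** Much of the case on the other side stands.

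- **No contradiction.** A reader might infer that excluding patients breaks the all-randomized rule. It does not: the rule admits specified exceptions, and section 6.4.1 is one.
- **The cell-count rule is a screening rule.** A reader might infer that Week 2 scores will be lost because "Samples must contain a minimum of 500 viable tumor cells". In section 4.5.10 that sentence belongs to the pretreatment sample, whose adequacy cannot depend on study drug. The Week 2 bullet asks for two FFPE cores and one frozen core and states no such minimum. Inadequate Week 2 tissue remains plausible, but no cited rule establishes it.
- **Early stopping may be rare.** The window is 14 days of single-agent oral treatment. Section 1.4.2 reports no withdrawals for adverse events in the preoperative study of similar length, although those data are small and preliminary.
- **Some safeguards exist.** The Day 15 biopsy is mandatory, tissue must go to the central laboratory whichever laboratory tests eligibility, and discontinuations are summarized by arm.
- **The scenarios are chosen.** A split of 9% versus 3% is threefold, and Step 2 treats all missingness, including missing baselines, as related to outcome.
- **The study is exploratory.** Section 6.8 calls it hypothesis-generating.

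These points limit the size and certainty of the problem. They do not supply the missing check: a summary of discontinuations does not show who lacks a Ki67 score or why, and no planned analysis varies the assumption about those patients.

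**Conclusion.** The primary result rests on an unstated assumption that missingness is unrelated to Ki67 change within each arm, and the plan contains nothing to test it. That is a gap in robustness, not a fatal flaw.

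A reader might go further and infer that the result will be biased. The documents do not support that. They assume the same 6% in both arms, they show neither informative nor differential missingness, and equal missingness with equal shifts leaves no bias. The direction is also unknown.

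Under the stated assumptions the distortion ranges from 8% of the target effect (7% versus 5% missing) to 23% (9% versus 3%), with missing patients 1 SD better than average. At 6% missing, overturning a result exactly at the design effect takes about a 2 SD one-arm shift. Results nearer the critical value, or missing rates above 6%, would be more fragile.

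**What to change.** Add the following to section 6.4.1 or the SAP, before any unblinded look, including the optional interim in section 6.8:

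1. **Constrained longitudinal model.** Analyze log(Ki67 + 0.1) at baseline and Week 2 with a common baseline mean across arms and the stratification factors, including every randomized patient with at least one central score. Use it as the primary analysis, or as a named sensitivity analysis beside the complete-case test. Patients with neither score contribute nothing and should be counted.
2. **One delta-adjusted tipping-point analysis.** Shift the missing Week 2 values separately by arm and report where the conclusion changes. This is needed because the longitudinal model assumes data are missing at random, so it cannot deal with strong responders who lack tissue for that reason.
3. **A table of missing baseline and Week 2 central Ki67 by arm, with reasons.**

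Report these beside the primary result, not as a gate on a positive claim; a gate would be out of proportion in a hypothesis-generating Phase II study.

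The sample size stays at 202 evaluable and 215 enrolled. The cost is extra SAP text and some programming on existing Ki67 and stratification data; the only addition is to document the reason for each missing score.

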6.4.2 Secondary Efficacy Endpoints

ORR will be defined as the proportion of patients with a CR or PR, as determined by the investigator according to mRECIST (see [Appendix 4](#)). The analysis population for ORR will be all randomized patients with measurable disease at baseline. Patients not meeting the criteria for ORR, including patients without any post-baseline tumor assessment, will be considered as non-responders.

An estimate of ORR and its 95% CI will be calculated using the Clopper-Pearson method for each treatment arm. ORR will be compared between treatment arms using the stratified Cochran-Mantel-Haenszel test. The stratification factors to be used will be the same as those used for randomization. The difference in ORR between treatment arms will be calculated, and its 95% CI will be calculated using the normal approximation to the binomial distribution.

CCCA rate is defined as the proportion of patients with centrally measured Ki67 score $\leq 2.7\%$. CCCA rate at Week 2 will be summarized. The difference in CCCA rates between treatment arms will be calculated, and its 95% CI will be calculated using the normal approximation to the binomial distribution. Patients with missing central baseline and/or Week 2 corresponding Ki67 score will be excluded from the analysis.

6.4.3 Exploratory Efficacy Endpoints

CCCA rate is defined as the proportion of patients with centrally measured Ki67 scores $\leq 2.7\%$. CCCA rate at surgery will be summarized. The difference in CCCA rates between treatment arms will be calculated, and its 95% CI will be calculated using the normal approximation to the binomial distribution. Patients with missing central baseline and/or Week 2 corresponding Ki67 scores will be excluded from the analysis.

pCR rate is defined as the proportion of patients who achieved pCR in breast and axilla (with pCR defined as the absence of any residual invasive cancer on hematoxylin and eosin evaluation of the resected breast specimen, and all sampled ipsilateral lymph nodes following completion of neoadjuvant systemic therapy [i.e., ypT0/is, ypN0 in the current American Joint Committee on Cancer staging system]) after completion of neo-adjuvant treatment.

The pCR rate will be analyzed using statistical methods similar to those used for ORR.

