2.1.3 Exploratory Efficacy Objective

The exploratory efficacy objective for this study is to evaluate the efficacy of GDC-9545 plus palbociclib compared with anastrozole plus palbociclib on the basis of the following endpoints:

- Central assessment of changes in Ki67 scores from baseline to surgery and from Week 2 to surgery
- CCCA rate as defined as proportion of patients with centrally assessed Ki67 scores $\leq 2.7\%$ stained nuclei upon treatment at surgery or post-treatment biopsy (see Section 4.5.10)
- Pathological complete response (pCR) rate (ypT0/is, ypN0) of GDC-9545 plus palbociclib compared with anastrozole plus palbociclib

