All patients will be required to provide a pretreatment tumor tissue sample during screening, a tumor biopsy sample during treatment, and a post-treatment tissue sample from the surgical specimen (see Section 4.5.10).

In the neoadjuvant treatment phase, before each cycle, a blood sample will be collected and physical examination performed (see Appendix 1 and Appendix 2). Tumor assessments by ultrasound are mandatory at screening, and an additional tumor assessment by ultrasound must be performed after the final dose of neoadjuvant combination treatment (i.e., after Day 21 of Cycle 4 and prior to surgery). If there is suspicion of disease progression, any other method to evaluate the disease will be allowed at any time at investigator's discretion (see Appendix 1).

Surgery must be performed within a maximum of 14 days after the final cycle in the neoadjuvant treatment phase and ideally should occur as soon as possible after the last dose of study treatment. A surgical specimen will be obtained for analysis and will be analyzed by the local pathologist. If surgery is delayed, the patient is not operable or will not undergo surgery for other reasons, or does not complete 16 weeks (four cycles) of combination therapy, an optional biopsy may be performed as a separate procedure within 2 days from the end of the combination treatment.

All patients must return for the end of study visit 28 days after the final dose of study treatment regardless of the reason for treatment discontinuation. Patients who experience disease progression or unacceptable toxicity will be treated as per local practice after the end of study visit.

[figure not shown]
Patient treatment after the surgery will be at the investigator's discretion. Systemic chemotherapy and radiation therapy, if indicated, may be initiated after the end of study visit. Any post-surgery treatments are not part of the study and will not be provided by the Sponsor, and data will not be collected.

Patient-reported outcome (PRO) instruments will be completed by patients to evaluate the experience of treatment from the patient's perspective as specified in the schedule of activities (see [Appendix 1](#)).

[Figure 1](#) presents an overview of the study design. A schedule of activities is provided in [Appendix 1](#) and [Appendix 2](#).

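### CCCA at surgery (Section 6.4.3) excludes patients on missing baseline or Week 2 Ki67 and sets no rule for a missing surgery score, including in patients with pCR

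*Combined protocol and SAP*

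**What the plan says.** Section 2.1.3 lists, as an exploratory endpoint, the share of patients with a central Ki67 score of 2.7% or less "stained nuclei upon treatment at surgery or post-treatment biopsy". Section 6.4.3 says this rate at surgery will be summarised, with a between-arm difference and a 95% CI by normal approximation. It then states: "Patients with missing central baseline and/or Week 2 corresponding Ki67 scores will be excluded from the analysis".

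Section 6.4.2 gives the rule for CCCA at Week 2: "Patients with missing central baseline and/or Week 2 corresponding Ki67 score will be excluded from the analysis". The two sentences differ only in singular versus plural.

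Other places bear on who has a surgery score and who is analysed:

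- Section 4.5.10: "If the patient has pCR at time of surgery, tumor surgical specimens will no longer required".
- Section 3.1, for delayed or omitted surgery or incomplete combination therapy: "an optional biopsy may be performed as a separate procedure within 2 days from the end of the combination treatment". Section 4.5.16 repeats that this biopsy is optional.
- Section 6: "Efficacy analyses will consist of all randomized patients, unless specified otherwise". Section 6.4 repeats it: "the analysis population for an efficacy analysis will consist of all randomized patients", again unless specified otherwise.
- Section 6.1 assumes that 6% of patients in each arm lack a baseline and/or Week 2 central score, which takes 202 evaluable patients to 215 enrolled.

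**The concern.** The exclusion is tied to timepoints that this endpoint does not use. Classifying a patient as CCCA at surgery needs only the surgery (or post-treatment biopsy) score. Baseline and Week 2 scores are needed for a different endpoint in Section 2.1.3, "Central assessment of changes in Ki67 scores from baseline to surgery and from Week 2 to surgery". Two things follow from the text as it stands.

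First, a patient with a valid surgery score is removed because another biopsy was missing or could not be scored.

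Second, a patient without a surgery score is not covered by any rule. The gap will not be random. It is expected in patients with pCR, who have the best pathological outcome, and possible in patients who are not operated on and decline the optional biopsy. The study is open-label, so a choice left until the data are in would be made by people who could see which way it moves the comparison.

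**Working it through.** **Step 1. Reproduce the plan's figures.** Inputs from Section 6.1: effect size 0.3, one-sided 10% level, 80% power, 1:1 allocation, 6% missing.

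- n per arm = 2(1.2816 + 0.8416)² / 0.3² = 100.2, rounded up to 101, so 202 in total (power at 101 per arm: 80.2%).
- Enrolment = 202 / 0.94 = 214.9, so 215.

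Both stated figures reproduce. The plan gives no figure for CCCA at surgery.

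**Step 2. Surgery scores lost to the baseline/Week 2 condition.**

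- Excluded at the planning rate: 215 × 0.06 = 12.9, about 13 (equally 215 − 202).
- Ratio of CI widths if all 13 had a surgery score: √(215/202) = 1.032, about 3%.

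Thirteen is the most that could be recovered at that rate. Some of these patients, for instance those who left before the Day 15 biopsy, may have no surgery score either. The 6% is a planning value for baseline and Week 2 combined, and the Week 2 share is not given.

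**Step 3. What the silence on missing surgery scores could mean.** For each arm, let r be the CCCA rate among scored patients, p the pCR rate (all pCR patients unscored), and u the fraction unscored for other reasons. With r and u equal in both arms:

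| Handling of unscored patients | Rate in one arm | Difference between arms |
|---|---|---|
| All unscored excluded | r | 0 |
| All unscored kept as non-CCCA | r(1 − u − p) | −r(p₁ − p₂) |
| pCR counted as CCCA, other unscored excluded | [p + r(1 − u − p)] / (1 − u) | (1 − r)(p₁ − p₂) / (1 − u) |

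Section 1.5.3 cites CCCA rates of 87% and 90% on palbociclib plus an aromatase inhibitor, used here for r. The documents give no pCR rate, so every p is an assumption. The value u = 6% is borrowed from the Week 2 planning rate, and it cancels from the second row's difference.

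Example with r = 0.87, u = 0.06, pCR 10% versus 5%:

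- Excluded: 87% versus 87%, difference 0.
- Kept as non-CCCA: 0.87 × 0.84 = 73.1% versus 0.87 × 0.89 = 77.4%, difference −4.35 points.
- pCR as CCCA: (0.10 + 0.7308)/0.94 = 88.4% versus (0.05 + 0.7743)/0.94 = 87.7%, difference +0.7 points.

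Range of the second reading, −r(p₁ − p₂):

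| Assumed pCR | r = 0.87 | r = 0.90 |
|---|---|---|
| 2% vs 1% | −0.9 | −0.9 |
| 5% vs 2% | −2.6 | −2.7 |
| 10% vs 5% | −4.35 | −4.5 |
| 10% vs 2% | −7.0 | −7.2 |

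For scale, the 95% half-width in the example at 101 per arm is 1.96 × √[(0.7308 × 0.2692 + 0.7743 × 0.2257)/101] = 11.9 points. With equal pCR in both arms the second reading lowers both rates and leaves the difference at 0.

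**The case against.** The best defence is that this is a slip of the pen. The word 'corresponding' suggests that the score at the matching timepoint was meant, with Week 2 left standing where surgery belonged. On that reading patients without a surgery score are excluded, and with equal CCCA among scored patients the difference is unbiased. This is plausible, but the sentence names Week 2, and under the repaired reading patients with pCR would drop out without the plan saying so. Their classification would still not be prespecified.

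A reader might infer more: that the plan scores unscored patients, and so the best pathological responders, as failures to reach cell cycle arrest. The documents do not support that. No section says it. Where the plan wants missing to count as failure it says so, as it does for ORR in Section 6.4.2. Its stated rules for missing central Ki67, in Sections 6.1, 6.4.1 and 6.4.2, are exclusions. The all-randomized default fixes a population and does not impute an outcome. Counting these patients as non-CCCA is therefore one possible reading and no more.

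It can also be said that a common set of patients with all Ki67 scores is a legitimate choice. It is, but Section 6.4.3 gives no such reason, and a common set for this endpoint would still have to name the surgery score.

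**Conclusion.** The rule in Section 6.4.3 is wrong as written. It uses the Week 2 condition for a surgery endpoint, discards valid surgery scores and says nothing on missing ones, although Section 4.5.10 makes a missing score expected after pCR.

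The certain part is small: at most about 13 of 215 patients at the 6% planning rate, and up to about 3% in CI width. The rest is an unspecified choice, not a demonstrated bias. Depending on the choice, the difference is unaffected, shifts slightly in favour of the arm with more pCR, or shifts by about 0.9 points per percentage point of excess pCR against that arm. These directions assume equal CCCA among scored patients and equal other missingness. Their sizes rest on assumed pCR rates and cited CCCA rates, and all the illustrated shifts lie inside the 11.9-point half-width.

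Severity is minor. The endpoint is exploratory with no planned test, pCR is analysed separately, and neither the primary analysis nor the 202/215 sample size is touched.

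**What to change.** In Section 6.4.3, replace the exclusion sentence for CCCA at surgery with: *Patients without a central Ki67 score at surgery or post-treatment biopsy will be excluded, except patients with pCR and no scorable invasive tumor, who will be classified as CCCA.*

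Report the number of missing scores by arm and reason, and add one sensitivity analysis that excludes the patients with pCR.

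The cost is one sentence, one missing-score summary and one extra table. No new data, procedures or patients are needed.
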